7.1.6.1 Tipping Point Analysis

The MI paradigm, as proposed by Rubin, does not require nor assume any specific assumption about the nature of the missing data. Further, imputations can be (theoretically) created under any assumption of missing mechanism. A two-way tipping point analyses will be conducted to evaluate the robustness of the analyses with MI under the MAR assumption. With the tipping point approach, several additional MI datasets are created, each departing slightly from the assumptions used in the original analysis. The intended result is to establish a certain point in which the new shifted imputations have “tipped”, or overturned, the original conclusions from the original analysis (i.e. a statistically significant result is now not statistically significant). The magnitude of the shift required to tip the analysis is then evaluated for plausibility; an

implausible shift will lead to the conclusion that the MI analysis is robust to departures from MAR assumption.

The tipping point exercise will be conducted only for MI analysis(es) that is/are statistically significant under the MAR assumption. Applicable MI analyses will be reassessed by shifting the imputed values for the treatment group by intervals of ± 0.5 for Pain NRS and ± 5 for WOMAC and Patient Global. An implausible shift parameter would be higher in magnitude than the observed difference in mean change in the associated outcome between the treatment and placebo groups.

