5. SAMPLE SIZE DETERMINATION

A sample size of approximately 725 subjects was initially selected for this study to yield 325 evaluable subjects per treatment group assuming 10% dropout.

One thousand Monte Carlo simulations generated baseline and follow-up data from a bivariate normal distribution for each treatment group and estimated the least squares difference between treatment and placebo in an outcome's change using a baseline-adjusted analysis of covariance (ANCOVA). The proportion of statistically significant results at $\alpha = 0.05$ was estimated as the approximate power for a sample size of 325 subjects per group.

The following assumptions were made based upon observed data in the Phase 2 dose-ranging studies (SM04690-OA-02 and SM04690-OA-04):

- For Pain NRS, assuming a baseline mean (standard deviation [SD]) of 6.0 (1.5), follow-up mean (SD) of 3.0 (3.0) for SM04690 and 3.8 (3.0) for placebo (presumed treatment difference -0.8), and a baseline to follow-up correlation of 0.25, power is estimated to be 93.5%.
- For WOMAC Function, assuming a baseline mean (SD) of 60 (14), follow-up mean (SD) of 30 (29) for SM04690 and 37.5 (29) for placebo (presumed treatment difference -7.5), and a baseline to follow-up correlation of 0.25, power is estimated to be 92.0%.
- For Patient Global Assessment, assuming a baseline mean (SD) of 55 (20), follow-up mean (SD) of 35 (27) for SM04690 and 42.5 (27) for placebo (presumed treatment

difference -7.5), and a baseline to follow-up correlation of 0.25, power is estimated to be 95.3%.

Based upon a blinded evaluation of aggregate data, sample size assumptions were reassessed, and additional Monte Carlo simulations generated. A sample size of approximately 500 subjects was re-estimated for this study to yield 225 evaluable subjects per treatment group assuming 10% dropout.

- For Pain NRS, assuming a baseline mean (standard deviation [SD]) of 6.0 (1.2), follow-up mean (SD) of 3.0 (2.4) for SM04690 and 3.8 (2.4) for placebo (presumed treatment difference -0.8), and a baseline to follow-up correlation of 0.25, power is estimated to be 94.3%.
- For WOMAC Function, assuming a baseline mean (SD) of 60 (12), follow-up mean (SD) of 30 (25) for SM04690 and 37.5 (25) for placebo (presumed treatment difference -7.5), and a baseline to follow-up correlation of 0.25, power is estimated to be 89.8%.

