7.1.6 Imputation of Missing Data

Sensitivity analysis will be performed using multiple imputation (MI) for the primary and secondary endpoints. Missing data will be imputed based upon the observed data for each outcome under the MAR assumption following the paradigm first developed by Rubin (Shafer, 1999). The imputation will adjust for the outcome's baseline data in a regression model with data

imputed independently for each timepoint. A total of 10 imputation datasets will be created and analyzed based upon accepted convention (Shafer, 1999). Error estimates of the multiple imputation itself, as well as an overall summary of the efficacy analysis, will be averaged across the 10 imputed datasets based upon Rubin's paradigm.

Specifically, let Q denote the imputed mean of an efficacy outcome Y subject to missing data at a given timepoint, where the estimate of that mean for any i^{th} imputation would be defined as function of both observed and missing such that

$$\widehat{Q^{(i)}} = E\left(Q^{(i)}|Y_{observed}, Y_{missing}^{(i)}, Y_{Baseline}, I(Group)\right), i = 1, \dots, 10.$$

After all 10 datasets have been imputed, the overall estimate of Q is a simple average defined as

$$\bar{Q} = \frac{\sum_{i=1}^{10} \widehat{Q^{(i)}}}{10}.$$

For this analysis using 10 imputed datasets, the variance of \bar{Q} is defined as

$$Var(\bar{Q}) = 1.1B + \bar{U}$$

where B is the between imputation variance and U is the within imputation variance:

$$B = \frac{1}{9} \sum_{i=1}^{10} \left(\widehat{Q^{(i)}} - \bar{Q} \right)^2;$$

$$\bar{U} = \frac{\sum_{i=1}^{10} U^{(i)}}{10}.$$

PROC MI in SAS® will be used to impute missing data assuming missingness is monotone in pattern. If a subject is missing a baseline record causing non-monotone missingness, all non-missing post-baseline records will temporarily be set to missing as well. After the 10 imputation datasets are created, the non-missing post-baseline will be merged back in, thus creating complete datasets where only the originally missing records were imputed. Imputations will be performed with a seed of 469010.

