9.2 Primary Efficacy Analysis

9.2.1 Main Analysis

Change over time in Pain NRS will be characterized using an MMRM model to estimate change from baseline with treatment group, week, treatment \times week interaction and baseline value as covariates. The model will include all timepoints for subjects in the FAS and will be evaluated at Week 12.

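### The tipping-point section announces a two-way analysis but shifts one arm only, and its coarse grid keeps marginal results from being tested at the section's own plausibility limit

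*SAP*

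**What the plan says.** SAP 7.1.6.1 opens with the aim: "A two-way tipping point analyses will be conducted to evaluate the robustness of the analyses with MI under the MAR assumption". The analysis is run only where the multiple-imputation (MI) result is significant under missing at random (MAR). The procedure consists of "shifting the imputed values for the treatment group by intervals of" 0.5 in either direction for Pain NRS and 5 for WOMAC and Patient Global. No shift is given for placebo. The same paragraph then contrasts the treatment and placebo groups, so treatment group there means the active arm.

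The decision rule has two parts. The limit is: "An implausible shift parameter would be higher in magnitude than the observed difference in mean change in the associated outcome" between the arms. The consequence is that an "implausible shift will lead to the conclusion that the MI analysis is robust to departures from MAR assumption". The section does not say whether the observed difference is raw or baseline-adjusted.

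In Appendix 3 (Estimands) the tipping-point step belongs to Sensitivity 1 for the primary endpoint and for each secondary endpoint listed. Sensitivities 2 and 3 deal with NSAID/acetaminophen use and the per-protocol set.

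**The concern.** There are two defects.

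First, the aim and the instruction disagree. Two-way could mean that both arms are shifted, or only that shifts run in both directions. On the second meaning, one direction cannot tip a favourable result, and departures that differ between the arms are not examined.

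Second, the limit is continuous but the search is not. The rule treats any shift up to d as plausible. A marginal Pain NRS result can have d below 0.5, and then no non-zero grid step lies within the limit. Such a result may lose significance at the first step and still be called robust, only because 0.5 exceeds d.

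This is the only planned check on departures from MAR, and marginal results are the ones for which it is needed.

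**Working it through.** **Inputs.** SAP 5, re-estimated design for Pain NRS: baseline and follow-up means (SD) of "6.0 (1.2), follow-up mean (SD) of 3.0 (2.4) for SM04690 and 3.8 (2.4) for placebo", correlation 0.25, and about 500 randomized "to yield 225 evaluable subjects per treatment group assuming 10% dropout". Two-sided alpha is 0.05. The missing share f = 0.10 is borrowed from the dropout allowance; the documents give no observed share. Imputation is taken to use baseline and group, as in the displayed formula of SAP 7.1.6. The tipping shift is taken as the first grid value at which significance is lost, without interpolation.

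**Reproducing the plan's power.**
- SE = 2.4 × √(1 − 0.25²) × √(2/225) = 0.2191.
- Power = Φ(0.8/0.2191 − 1.96) = Φ(1.691) = 95.5%, against the stated 94.3% from 1,000 simulations.
- The Monte Carlo error of the stated figure is √(0.943 × 0.057/1000) = 0.7 points, so the two agree well enough. 450/0.9 = 500 also reproduces.

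**The band that the limit overturns.** Shifting a fraction f of active-arm values by s against the drug lowers the benefit from d to d − f·s.
- Significance boundary: 1.96 × 0.2191 = 0.429.
- A shift of exactly d overturns the result if d(1 − f) < 0.429, i.e. d < 0.429/0.9 = 0.477. That is z < 2.178, p > 0.029.
- The band is therefore 0.429 < d < 0.477, all of it below the first step of 0.5. By the normal approximation 100% of it is labelled robust.

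**Example, d = 0.45.**
- Unshifted: 0.45/0.2191 = 2.054, p = 0.040.
- At 0.5: (0.45 − 0.05)/0.2191 = 1.826, p = 0.068. The result tips but is called robust because 0.5 > 0.45.
- At 0.25: 0.425/0.2191 = 1.940, p = 0.052. With that step the same data would not be called robust.

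**Finer steps alone.** A 0.25 step catches only d < 0.429 + 0.1 × 0.25 = 0.454. The rest of the band, (0.477 − 0.454)/(0.477 − 0.429), or 48%, is still mislabelled. A 0.1 step leaves 16%.

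**How many results are affected** (share of significant Pain NRS results in the band):
- True effect 0.8: P(significant) = 0.955 and P(d > 0.477) = Φ((0.8 − 0.477)/0.2191) = 0.930, so (0.955 − 0.930)/0.955 = 2.6%.
- True effect 0.4: 0.447 and 0.362, so (0.447 − 0.362)/0.447, or 18.9% from unrounded values.
- An observed d of 0.8 tips only at (0.8 − 0.429)/0.1 = 3.7 points.

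**Simulation of the MI** (250 per arm, random missingness, ten imputations, Rubin pooling). Among Pain NRS results overturned by a shift of d, 73-93% are labelled robust at 10% missing. The range covers raw and adjusted d and both effect sizes. It falls short of 100% because the standard error varies between trials, so some affected results have d above 0.5.

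**Other missing shares.**

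| Missing | Normal approximation | Simulation |
|---|---|---|
| 10% | 100% | 73-93% |
| 15% | 78% | 55-68% |
| 20% | 51% | 43-54% |

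**WOMAC Function** (SD 25, 10% missing): SE = 2.282 and the band is 4.47 to 4.97, again wholly below its step of 5. The simulated share is 64-79%. SAP 5 gives no re-estimated inputs for Patient Global, so it is left out.

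**Two arms.** With upward (worse) shifts s_a and s_p and missing shares f_a and f_p, the benefit becomes d − f_a·s_a + f_p·s_p. If the shares are equal, only s_a − s_p matters, and a one-arm shift can stand in for it, though the limit still caps it at d. If the shares differ, even a common shift moves the result by (f_a − f_p)·s, which a one-arm search does not show.

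**The case against.** The strongest objection is reach. The band holds about 2.6% of significant Pain NRS results at the planned effect. The 19% figure needs half that effect, which is not a planning value. The tipping shift itself can be reported, so a reader would see that a result with d = 0.45 tipped at 0.5. The section also speaks of evaluating plausibility, which leaves room for judgement. All of this limits the importance of the point. It does not repair the rule, because the stated consequence of exceeding d is a conclusion of robustness.

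Three stronger readings are tempting, and the documents do not support them:
- *The SAP has settled on shifting one arm.* The operative sentence reads that way, but the opening sentence says two-way. This is an inconsistency to reconcile.
- *Most marginal results are mislabelled whatever the missingness.* The share is about half at 20% missing. It also depends on the significance boundary lying below the step: with SD 3.0 and only 250 per arm the boundary is 0.537 and the share is about 16%.
- *Return to baseline is the required reference.* The MI has each outcome "imputed independently for each timepoint" from baseline, whereas for the MMRM "The model will include all timepoints for subjects in the FAS and will be evaluated at Week 12". Withdrawal that follows recorded pain may thus be MAR for one and not for the other. That argues for adding interim scores to the imputation model; it does not show that dropouts go back to baseline. SAP 7.1.2 notes that the injection cannot be removed, and under SAP 7.3.1 a week is also missing when fewer than four diary days were completed.

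**Conclusion.** The point holds in a limited form. SAP 7.1.6.1 contradicts itself on what is shifted, and its grid prevents the rule from applying its own limit. At 10% missing on the re-estimated inputs, Pain NRS results with p of about 0.029 to 0.05 would be overturned by a shift of d, yet nearly all are called robust: 100% by the normal approximation, 73-93% in simulation.

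This rests on the dropout allowance standing in for Week 12 missingness, on the SD of 2.4, on imputation using baseline and group, and on the tipping shift being the first non-significant grid value. A reader might infer that the primary conclusion is at risk. It is not: the primary MMRM and the fixed testing sequence do not use this rule, and an observed difference near the planned 0.8 is far from tipping. What is at stake is whether a robustness statement about a marginal result can be trusted.

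**What to change.** In SAP 7.1.6.1:

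1. Test the limit directly, at a shift of exactly d in the active arm, and base the robustness statement on that test. Finer steps alone do not suffice.
2. Define d as the baseline-adjusted difference from the MI analysis.
3. State what two-way means. Shift active and placebo imputed values independently on a two-dimensional grid with finer steps, for example 0.25 for Pain NRS and 2.5 on the 0-100 scales.
4. Report the tipping frontier and the missing share by arm.

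Return to baseline may be added as an optional reference.

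The cost is a few sentences of SAP text and a longer loop in the same program. The downsides are more output and the chance that a marginal result loses its robust label. The primary analysis and the testing order do not change.

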7.2 Interim Analysis

There is no planned interim analysis for this study.

7.3 Efficacy Assessments

7.3.1 Pain NRS

The Pain NRS is an 11-point scale [0-10] for subject self-reporting of average knee pain in the previous 24 hours, where 0 represents no pain and 10 represents extreme pain. Subjects were prompted to report average pain in both knees daily on their electronic device (between 5:00 pm and 11:59 pm) during the screening period and on the target knee only starting from Day 1 through the end of the study. An average weekly score (referred to as Pain NRS) was calculated for each subject if they had provided a response for at least 4 out of 7 days in a given week. Weeks are defined as Day -7 through Day -1 (day before treatment) for baseline, Day 1 (day of treatment) through Day 7 for Week 1, Day 8 through Day 14 for Week 2, and so on as detailed in [Appendix 1](#). The day on which subjects completed their scheduled study visits (e.g. Week 4 Visit, Week 12 Visit, etc.) does not impact the above definition of weeks.

7.3.2 WOMAC

The WOMAC is a widely used, proprietary outcome measurement tool used by health professionals to evaluate the condition of patients with OA of the knee and hip, including pain, stiffness, and physical functioning of a target joint. The WOMAC Version NRS 3.1 was to be completed by the subject for their target knee in the evening (between 5:00 pm and 11:59 pm) remotely on their electronic device 5 days after their Screening Visit or up until the day before the Day 1 visit. After Day 1, WOMAC assessments were to be completed by the subject for their target knee in the evening (between 5:00 pm and 11:59 pm) remotely on their electronic device at Week 4 (with a window of ± 3 days) and Weeks 12, 24, and 28 (with windows of ± 7 days). The devices required subjects to enter a response for each item before proceeding to the next. If an assessment was completed more than once within a window, only the first assessment will be used for analysis. All visit windows are detailed in [Appendix 1](#).

WOMAC consists of 24 questions in three domains: physical function (17 questions), pain (5 questions) and stiffness (2 questions). The response for each question in the NRS format ranges from 0 to 10. Each domain subscore as well as a total score are calculated by adding together the numerical responses for a range of 0 to 240 total points. For analysis, WOMAC scores will be linearly transformed to a 0-100 scale, where 0 represents no difficulty and 100 represents extreme difficulty.

7.3.3 Patient Global Assessment of Disease Activity

The Patient Global Assessment is an 11-point [0-10] NRS on which the subjects rated how they felt their target knee OA was doing, considering all the ways in which their target knee OA may have affected them. The NRS was anchored by descriptors at each end (“Very Good” on the left and “Very Bad” on the right). The Patient Global Assessment was to be completed by the subject in the evening (between 5:00 pm and 11:59 pm) remotely on their electronic device 5 days after their Screening Visit or up until the day before the Day 1 visit. After Day 1, Patient Global Assessments were to be completed by the subject in the evening (between 5:00 pm and 11:59 pm) remotely on their electronic device at Week 4 (with a window of \pm 3 days) and Weeks 12, 24, and 28 (with windows of \pm 7 days). If an assessment was completed more than once within a window, only the first assessment will be used for analysis. All visit windows are detailed in [Appendix 1](#). For analysis, Patient Global Assessment scores will be scaled to 0-100, where 0 represents “Very Good” and 100 represents “Very Bad”.

7.3.4 NSAID/Acetaminophen Usage

Information about NSAID and acetaminophen usage was collected as part of concomitant medications at all visits. Subjects were asked to recall the name, usual total daily dose, and usual number of days taken per week of any NSAID or acetaminophen during the previous 4 weeks. Assessment of NSAID/acetaminophen usage on Day 1 prior to study medication administration will be used to establish the subject’s baseline 4-week NSAID/acetaminophen usage.

Starting at Week 4 and at all subsequent in-person and phone visits until Week 28 [End of study (EOS)] or ET, subjects were asked about their NSAID/acetaminophen usage during the previous 4 weeks. This information (name, usual total daily dose, usual number of days taken per week) was documented as concomitant medications. The Investigator then compared the data with the baseline information obtained on Day 1. If there was a change from baseline, the Investigator first assessed whether the change was clinically relevant and, if clinically relevant, whether it was due to the subject’s target knee OA pain.

7.4 Safety Assessments

7.4.1 Adverse Events

An AE is any unfavorable and unintended sign, symptom, or disease temporally associated with the use of an IP or other protocol-imposed intervention, regardless of attribution. Signs and symptoms of exacerbation or worsening of target knee OA were captured in the context of efficacy assessments. Anticipated fluctuations or anticipated deterioration (in the opinion of the Investigator) of the underlying disease (target knee OA) were not considered as AEs.

Severity was assessed utilizing the CDISC AESEV, which classifies AEs as mild, moderate, or severe. For analysis, relationship will be dichotomized into Unrelated (combining Not Related and Unlikely Related) and Related (combining Possibly Related and Probably Related).

7.4.2 Vital Signs and Weight

Vital signs were measured by a qualified staff member at Screening Visit, Day 1, and Weeks 4, 12, 24, and 28 (EOS) or ET. At each time point, the following vital were measured:

- Body temperature

- Pulse rate
- Respiratory rate
- Blood pressure (systolic and diastolic) after the subject rests (sitting or supine) for at least 5 minutes

Any measurement that was, in the opinion of the Investigator, abnormal AND clinically significant was considered as medical history if found prior to study medication injection or as an AE if found after study medication injection.

Weight measurements will be taken at the Screening Visit and at Week 28 (EOS) or ET.

7.4.3 Clinical Laboratory Evaluations

Fasting specimens for clinical laboratory analysis were to be collected at Screening Visit and Weeks 4, 12, 24, and 28 (EOS) or ET. At a minimum, the following tests were conducted:

- **Chemistry panel:** Albumin, alkaline phosphatase, alanine aminotransferase, aspartate aminotransferase, blood urea nitrogen, bicarbonate, calcium (corrected total), chloride, creatinine, glucose, lactate dehydrogenase, potassium, sodium, bilirubin (total)
- **Hematology:** Hemoglobin, hematocrit, red blood cell count, white blood cell count with differential, and platelet count
- **Urinalysis:** Clarity, specific gravity, pH, protein, glucose, ketones, nitrite, leukocyte esterase, and occult blood

Urine microscopy was to be performed if urinalysis urine protein, leukocyte esterase, occult blood, or nitrite values were out of range, or if the Investigator deemed that the microscopy was clinically warranted

8. STUDY SUBJECTS AND DEMOGRAPHICS

8.1 Disposition of Subjects and Withdrawals

Subject disposition will be presented in a summary table detailing the number and percentage of subjects who were consented, randomized, treated, completed the study, or discontinued (e.g. adverse event, subject decision, etc.) overall and by treatment group. Additionally, subject disposition for randomized subjects will be presented by treatment group and study site.

Additional tables will be prepared to summarize the number of subjects enrolled under each protocol version and included in each analysis set. The disposition for individual subjects will be listed along with additional information on discontinued and screen failed subjects.

8.2 Protocol Deviations

A protocol deviation is defined as any noncompliance with the clinical trial protocol requirements. The noncompliance may be either on the part of the subject, the Investigator, or the study site staff.

Deviations are summarized into one of the following categories:

- Informed Consent Form
- Enrollment

- Procedures
- Labs/Specimens
- Study Visits
- Investigational Product
- Subject Non-Compliance
- Serious Adverse Events

Deviations are categorized as major or minor by a cross-functional team according to pre-defined criteria established in the Protocol Deviation Classification Guideline.

- A major deviation is defined as a divergence from the protocol that materially (a) reduces the quality or completeness of efficacy data, (b) makes the informed consent inaccurate, or (c) impacts a subject's safety, rights or welfare.
- A minor deviation is defined as a divergence from the protocol that deviates from the procedures and guidelines outlined in the protocol, but is not classified as a major deviation (i.e. the deviation does not materially (a) reduce the quality or completeness of the data, (b) make the informed consent inaccurate, or (c) impact a subject's safety, rights or welfare).

Protocol deviations may result in subject exclusion from the PPAS. Prior to unblinding, all protocol deviations were reviewed by blinded study team members to determine if the deviation could reasonably affect/confound interpretation of key efficacy endpoints and should result in the subject being excluded from the PPAS. 26 subjects with the following types of deviations were excluded from PPAS:

- Major EN01 deviations (subject randomized or enrolled without meeting eligibility criteria) related to the following:
 - Pain NRS, WOMAC Pain, or WOMAC Function: n = 4
 - Medications that may impact pain assessment at baseline: n = 5
 - Significant malalignment of anatomical axis of the target knee by radiograph: n = 7
- Major NC04 deviations (prohibited concomitant medication taken) that would affect efficacy analysis at Weeks 12 or 24: n = 9
- Major SV01 deviations (Study visit out of window) where an out of window Screening Visit impacts baseline WOMAC Pain or WOMAC Function: n = 1

A final list of protocol deviations resulting in subject or data exclusion from the PPAS can be found in [Appendix 2](#).

Major protocol deviations will be summarized by site and category, and all protocol deviations will be listed for each subject. Additionally, the COVID-19 pandemic related protocol deviations will be summarized separately.

If the radiograph prior to study entry was rated unacceptable by central imaging vendors and repeat radiographs were also rated unacceptable, the first radiograph will serve as the baseline assessment.

